BSA=Body Surface Area; CV=cardiovascular; DLQI=Dermatology Life Quality Index; ECG=electrocardiogram; eCRF=electronic Case Report Form; eC-SSRS=electronic Columbia Suicide Severity Rating Scale; EQ-5D-3L=Euro-Quality of Life 5-Dimensions 3 Levels; GI=gastrointestinal; HCV=hepatitis C virus; HIV=human immunodeficiency virus; ICF=Informed Consent Form; IGA=Investigator’s Global Assessment; IGRA=interferon-gamma release assay; IMP=investigational medicinal product; IRT=interactive response technology; mNAPSI=Modified Nail Psoriasis Severity Index Score; PASE=Psoriatic Arthritis Screening and Evaluation; PASI=psoriasis area severity index; PEOT=Premature End of Treatment Visit; PGADA=Patient Global Assessment of Disease Activity; PHQ-9=Patient Health Questionnaire-9; pp-IGA=palmoplantar Investigator’s Global Assessment; PsA=psoriatic arthritis; SF-36=Short Form 36-item Health Survey; SFU=Safety Follow-Up; scalp IGA=scalp-specific Investigator’s Global Assessment; TB=tuberculosis; WPAI-SHP=Work Productivity and Activity Impairment Questionnaire-specific health problem

^a Visit windows of ±3 days from the first dose to the Week 24 visit. Visit windows of ±7 days from the Week 28 visit to the Week 52 visit. The SFU Visit window is ±7 days from final dose.

^b The SFU Visit will occur 20 weeks after the final dose for subjects who do not enroll in the open-label study.

^c All genomic, proteomic, and metabolomics samples will be stored at -80°C at the central biorepository for up to 20 years.

^d A separate ICF is required to be completed for the open-label study.

^e Ensure no significant changes in medical history.

Table 5–1: Schedule of study assessments

Visit ^a / Week	Screening	Double-blind Initial Treatment Period (weeks after first dose)										Dose-blind Maintenance Treatment Period (weeks after first dose)										W56/PEOT	SFU ^b				
		Baseline (first dose)	1	3	4	5, 7	8	9, 11	12	13, 15	16	17, 19	20	21, 23	24	28	32	36	40	44	48			52	56		
Protocol activity																											

^f Includes evaluation of signs and symptoms of active TB and risk for exposure to TB.

^g The physical examination will be performed as per [Section 12.3.5](#).

^h Vital signs (sitting systolic and diastolic blood pressure, pulse rate, and body temperature) are to be measured prior to blood sampling, and prior to dosing, where applicable.

ⁱ Pregnancy testing will consist of serum testing at the Screening. The pregnancy test will be urine at all other visits.

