7.2 Treatment(s) to be administered

Unblinded study staff will be responsible for preparation of the clinical study material, including recording the administration information on source documents, and administration of the IMP as sc injections. The unblinded personnel will not be involved in the study in any way other than assuring the medication is taken from the correct kit and administering the IMP to the subjects.

Suitable areas for sc injections are the lateral abdominal wall and upper outer thigh. During each dosing visit, each of the injections should be administered at a separate injection site. Injection sites should be rotated at each visit and injections should not be given into a PSO plaque or areas where the skin is tender, bruised, erythematous, or indurated. The injection should last approximately 10 to 15 seconds.

An IMP Handling Manual will be provided to each site containing instructions regarding drug preparation and dosing.

Eligible subjects will be randomized 1:1:1 to receive the following blinded study treatment regimens: bimekizumab 320mg Q4W throughout the study, bimekizumab 320mg Q4W until Week 16, or adalimumab.

Because of differences in the dosing schedule between bimekizumab and adalimumab and in order to maintain blinding, all subjects will receive 2 injections sc on Weeks 0 (Baseline), 4, 8, 12, 16, 20, and 24, and 1 injection sc in other weeks:

- Subjects randomized to receive bimekizumab 320mg Q4W throughout the study will receive 2 bimekizumab 160mg injections sc Q4W at Weeks 0 (Baseline), 4, 8, 12, 16, 20, 24, 28, 32, 36, 40, 44, 48, and 52. These subjects will receive 1 placebo injection at Weeks 1, 3, 5, 7, 9, 11, 13, 15, 17, 19, 21, and 23.
- Subjects randomized to receive bimekizumab 320mg Q4W/Q8W will receive 2 bimekizumab 160mg injections sc Q4W at Weeks 0 (Baseline), 4, 8, and 12. Subjects will then receive 2 bimekizumab 160mg injections sc Q8W at Weeks 16, 24, 32, 40, and 48. These subjects will receive 1 placebo injection at Weeks 1, 3, 5, 7, 9, 11, 13, 15, 17, 19, 21, and 23, and 2 placebo injections at Weeks 20, 28, 36, 44, and 52.

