2.3.2.3 Dose-blind Maintenance Treatment Period

After the 16-week Initial Treatment Period, subjects will enter the 40-week Maintenance Treatment Period. Treatment during the Maintenance Treatment Period will start with the first study drug administration on or after Week 16 and subjects will return to the clinic Q4W or Q8W through Week 56. The IMP will be administered in the clinic by sc injection at the time points specified in the schedule of study assessments.

Treatment during the Maintenance Treatment Period will be based on initial treatment per the following:

- Subjects in the bimekizumab 320mg Q4W treatment arm will continue to receive bimekizumab 320mg Q4W.
- Subjects in the bimekizumab 320mg Q4W/Q8W treatment arm will receive bimekizumab Q8W from Week 16 through Week 52.
- Subjects in the adalimumab treatment arm will receive bimekizumab 320mg Q4W from Week 24 to Week 52.

Subjects may receive placebo injections at certain visits in order to blind the IMP.

At the end of the Maintenance Treatment Period, all subjects enrolling in the open-label study will, after signing a new ICF, undergo the Week 56 study assessments and then receive their first dose of bimekizumab in the open-label study. All subjects not enrolling in the open-label study will have the Week 56 study assessments and will enter the SFU Period.

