10.1 Extent of exposure

Summaries for exposure will be provided. This consists of a descriptive summary of study medication duration in days. In addition, total study medication duration and time at risk will be summarized in years by treatment group and treatment period (i.e., through initial treatment period, Week 24, and initial and maintenance treatment period). The summary of exposure through the initial and maintenance treatment period will be on BKZ set. The cumulative study medication duration will be summarized for subjects exposed for given durations of time, with four weekly categories through initial treatment period and Week 24. For the cumulative duration through initial and maintenance treatment period the following categories for duration will be used:

- >0 weeks
- ≥ 16 weeks
- ≥ 24 weeks
- ≥ 40 weeks
- ≥ 56 weeks

Definitions for study medication duration and time at risk in days are provided below for each period. Time at risk will be summarized in years. Time at risk in years is calculated by dividing the time at risk in days by 365.25.

Throughout this section, date of last clinical contact for each subject is defined as the maximum of (last visit date including SFU visit, last imputed AE start date, date of study termination or completion, last date of study drug administration).

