10.1.1 Exposure during the initial treatment period for SS

Definitions for study medication duration (days) and time at risk (days) during the initial treatment period are provided as follows:

Study medication duration (days)

- Date of last dose of active medication in the Initial treatment Period – date of first dose in the Initial Treatment Period + 28 days for bimekizumab Q4W/ +14 days for adalimumab

Note: If date of last dose of active medication in the Initial Treatment Period + 28 days/ 14 days extends to a date beyond the date of the first dose in the Maintenance Treatment Period, then this calculation reverts to:

- Date of first dose in the Maintenance Treatment Period – date of first dose in the Initial Treatment Period + 1.

Note: For subjects who die during the Initial Treatment Period, if date of last dose of active medication in the Initial Treatment Period + 28 days/ 14 days extends to a date beyond the date of death, then this calculation reverts to:

- Date of death – date of first dose in the Initial Treatment Period + 1.

For subjects who permanently discontinue study treatment:

- Date of last dose of active medication – date of first dose + 28 days for bimekizumab Q4W/ +14 days for adalimumab.

Note: If date of last dose of active medication + 28 days/ 14 days extends to a date beyond the final visit date (including PEOT, but not including SFU), then this calculation reverts to:

- Final visit date (including PEOT, but not including SFU) – date of first dose + 1.

Time at risk (days)

- For subjects who complete the final visit of Initial Treatment Period and continue into the Maintenance Treatment Period: Date of first dose in the Maintenance Treatment Period – date of first dose in the Initial Treatment Period + 1.
- For subjects who discontinue on or prior to the final visit of the Initial Treatment Period, use the minimum of the following:
 - Date of last dose of Initial Treatment Period – date of first dose in the Initial Treatment Period + 140 days.
 - The total number of days in the Initial Treatment Period.
 - Date of last clinical contact – date of first dose in the Initial Treatment Period + 1.
- For subjects who die prior to the final visit of the Initial Treatment Period: Date of death – date of first dose in Initial Treatment Period +1.

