10.1.2 Exposure through Week 24 (not including Week 24 Visit) for SS

Definitions for study medication duration (days) and time at risk (days) through Week 24 are provided as follows:

Study medication duration (days)

- Date of last dose of active medication prior to Week 24 Visit – date of first dose in the Initial Treatment Period + 28 days for bimekizumab Q4W/ +56 days for bimekizumab Q8W/ +14 days for adalimumab.

Note: If date of last dose of active medication prior to Week 24 + 28 days/ 56 days/ 14 days extends to a date beyond the date of the first dose on or after Week 24, then this calculation reverts to:

- Date of first dose on or after Week 24 – date of first dose in the Initial Treatment Period + 1.

Note: For subjects who die during the first 24 weeks, if date of last dose of active medication prior to Week 24 + 28 days/ 56 days/ 14 days extends to a date beyond the date of death, then this calculation reverts to:

- Date of death – date of first dose in the Initial Treatment Period + 1.

For subjects who permanently discontinue study treatment:

- Date of last dose of active medication – date of first dose + 28 days/ 56 days/ 14 days
- Note: If date of last dose of active medication + 28 days/ 56 days/ 14 days extends to a date beyond the final visit date (including PEOT, but not including SFU), then this calculation reverts to:

Final visit date (including PEOT, but not including SFU) – date of first dose + 1.

Time at risk (days)

- For subjects who complete through Week 24 and continue beyond Week 24: Date of first dose on or after Week 24 – date of first dose in Initial Treatment Period + 1.
- For subjects who discontinue prior to Week 24 visit, use the minimum of the following:
 - Date of last dose prior to Week 24 – date of first dose in the Initial Treatment Period + 140 days.
 - The total number of days up to Week 24.
 - Date of last clinical contact – date of first dose in the Initial Treatment Period + 1.
- For subjects who die prior to Week 24 visit: Date of death – date of first dose in Initial Treatment Period +1.

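### For identical attendance, SAP 10.1.1 and 10.1.2 give bimekizumab completers the same or less study medication duration than adalimumab completers, and the likely top exposure rows have no visit-window tolerance

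*SAP*

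**What the plan says.** For subjects who continue, SAP 10.1.1 takes the last active dose in the initial period minus "date of first dose in the Initial Treatment Period + 28 days for bimekizumab Q4W/ +14 days for adalimumab". If last dose plus interval falls after the first maintenance dose, the value becomes "Date of first dose in the Maintenance Treatment Period – date of first dose in the Initial Treatment Period + 1". SAP 10.1.2 applies the same construction to Week 24, with "28 days for bimekizumab Q4W/ +56 days for bimekizumab Q8W/ +14 days for adalimumab" and the first dose on or after Week 24 as the cut-off. SAP 10.1.3, for the BKZ Set, adds 28 days to the last bimekizumab dose (56 days in the Q4W/Q8W arm if that dose was in maintenance) and cuts off at the final visit plus one day.

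The first maintenance dose need not be active: "Treatment during the Maintenance Treatment Period will start with the first study drug administration on or after Week 16" (SAP 2.3.2.3). At Week 16 the adalimumab arm receives placebo (protocol 7.2).

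SAP 10.1 tabulates cumulative duration "with four weekly categories through initial treatment period and Week 24". For the initial and maintenance periods combined it names rows up to 56 weeks or more.

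Both 10.1.1 and 10.1.2 have a further line introduced by "For subjects who permanently discontinue study treatment". It uses last active dose minus first dose plus the interval, cut off at the final visit, and names no period.

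**The concern.** An exposure table should differ between arms only where treatment received differs. Here the interval added to the last dose carries adalimumab past the cut-off by a week but brings bimekizumab exactly to it. The two arms are then measured by different parts of the same rule. If the table's top category sits on bimekizumab's nominal value, a difference of a day or two can become a visible gap in the proportion shown as fully exposed. A safety reader could take that gap for poorer treatment completion on bimekizumab. The discontinuer line raises a separate question: whether later exposure could be counted inside an earlier period.

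**Working it through.** The documents state no expected exposure percentage, so there is no figure to reproduce. As a check on the dosing scheme, 14 two-injection visits and 12 one-injection visits give 40 injections, and 3 × 2 + 4 × 1 = 10 by Week 8. Both match SAP section 7.

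**Inputs**
- Bimekizumab Q4W active doses: "2 bimekizumab 160mg injections sc Q4W at Weeks 0 (Baseline), 4, 8, 12, 16, 20, 24, 28, 32, 36, 40, 44, 48, and 52" (protocol 7.2). The last before Week 16 is Week 12, the last before Week 24 is Week 20, and the last overall is Week 52.
- Bimekizumab Q4W/Q8W: the last active dose before Week 24 is Week 16, and the last overall is Week 48.
- Adalimumab: Week 15 before Week 16, Week 23 before Week 24.
- "Visit windows of ±3 days from the first dose to the Week 24 visit" (protocol Table 5–1, footnote a); ±7 days from Week 28 to Week 56 (SAP 3.1).
- Attendance within the windows: not given. Protocol section 8 asks sites to hold to the original dosing schedule.

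**Formulas.** Let d be days off schedule at the named week. In whole days, the rule equals the smaller of the two expressions.
- Week 16, bimekizumab: min(84 + d12 + 28, 112 + d16 + 1) = min(112 + d12, 113 + d16).
- Week 16, adalimumab: 105 + d15 + 14 = 119 + d15 always exceeds 112 + d16 within ±3 days, so the value is 113 + d16.
- Week 24, bimekizumab: min(168 + d20, 169 + d24) on Q4W, or min(168 + d16, 169 + d24) on Q4W/Q8W.
- Week 24, adalimumab: 169 + d24.
- Week 56, arms randomized to bimekizumab: min(392 + d52, 393 + d56), with d48 in place of d52 on Q4W/Q8W.

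**Duration.** On an exact schedule: 112 against 113 days, and 168 against 169. Over all in-window combinations at Week 16, bimekizumab is 0 to 7 days shorter. It is equal in 21/49 = 43% of equally weighted combinations, and 113.00 − 111.29 = 1.71 days shorter on average.

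**Rows.** Take the top rows as 112 and 168 days (inferred from the four-weekly wording). Bimekizumab needs d12 ≥ 0 and d16 ≥ −1; adalimumab needs only d16 ≥ −1. With independent uniform attendance this is 4/7 × 5/7 = 40.8% against 5/7 = 71.4%. The explicit 56-week row is 392 days: 8/15 × 9/15 = 32.0%.

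Other attendance assumptions for completers (normal SDs are for the ±3-day and ±7-day windows, on whole days within the window; gaps are taken before rounding):

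| Attendance | Bimekizumab ≥16 wk | Adalimumab ≥16 wk | Gap, points | ≥56 wk |
|---|---|---|---|---|
| Exact | 100% | 100% | 0 | 100% |
| SD 1/2 days, centred 1 day late | 93.7% | 99.5% | 5.9 | 69.6% |
| 80% exact, 20% uniform | 86.2% | 94.3% | 8.1 | 83.4% |
| SD 0.5/1 days | 89.3% | 100.0% | 10.7 | 65.9% |
| Same offset at both visits, uniform | 57.1% | 71.4% | 14.3 | 53.3% |
| SD 1/2 days | 65.9% | 94.2% | 28.3 | 46.5% |
| Triangular | 50.8% | 81.2% | 30.5 | 37.8% |
| Uniform | 40.8% | 71.4% | 30.6 | 32.0% |
| SD 1.5/3 days | 54.1% | 85.2% | 31.1 | 39.4% |
| SD 1/2 days, centred 1 day early | 21.2% | 70.3% | 49.1 | 24.0% |

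The 24-week figures are the same under the independent-visit assumptions, for both bimekizumab regimens. The 56-week column covers only completers randomized to bimekizumab. SAP 3.6 shows the BKZ Set as Q4W, Q8W and Total, and the Q4W column also takes Q4W/Q8W subjects to Week 16 and adalimumab switchers after Week 24. Neither group can reach 56 weeks in that column. Under uniform attendance and full completion it would show 0.32 × 150/450 = 10.7%, and Total 0.32 × 300/450 = 21.3%.

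**Discontinuers.** Read literally, a Q4W subject whose last dose is at Week 40 gets up to 280 + 28 = 308 days under the initial-period rule, less if the final visit comes sooner.

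**The case against.** The strongest reply concerns size. The documents give windows, not attendance, and tight attendance shrinks the gap to between 0 and about 11 points. The 16- and 24-week rows are inferred, because SAP 10.1 names such rows only for the BKZ Set, which has no adalimumab column. Mean duration differs by a day or two. The exposure-adjusted rates in SAP 10.2.1 rest on time at risk, and for continuing subjects the 10.1.1 and 10.1.2 definitions of time at risk are the same in every arm. All of this stands and limits the point to a descriptive table. It does not remove the asymmetry, which needs no attendance assumption, or the lack of tolerance at 56 weeks, where the row is explicit.

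One might also remove the asymmetry by running duration to the next-period dose in every arm. That would credit missed doses: a bimekizumab subject who missed Week 12 but was dosed at Week 16 would move from 56 + 28 = 84 days to 113. The objection to that remedy is sound, and last active dose plus interval should stay.

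On discontinuers, the 10.1.1 line sits under an initial-period heading and offers no 56-day interval, so the intended meaning is probably stops within the period. That makes it a missing phrase, but one that also occurs in 10.1.2, where the 56-day interval is offered.

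**Conclusion.** The point holds for the descriptive exposure table. Identical in-window attendance gives bimekizumab the same or less duration: one day less on an exact schedule, and about 1.7 days less on average if visits spread evenly. If the top rows are 16 and 24 weeks or more, they lie on bimekizumab's nominal duration and can show a gap produced by the formula. Across the scenarios run, that gap is 0 to 49 points, and 24% to 100% of completers randomized to bimekizumab reach 56 weeks. These are illustrations, not bounds.

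A reader might infer that the bimekizumab rows will read about 30 points lower and that only a third of completers will reach 56 weeks. The documents do not support either as a prediction. The first needs roughly symmetric, independent spread of SD 1 day or more; the second needs visits spread almost evenly over ±7 days. Nor is bimekizumab capped at 112 days: with Weeks 12 and 16 both 3 days late, the rule gives 115. The 56-week row offers no comparison with adalimumab, and no exposure-adjusted event rate changes.

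**What to change.** - In SAP 10.1, place the top categories inside the visit window, for example 15, 23 and 52 weeks or more, alongside the existing rows if wanted. The lowest in-window bimekizumab values are 112 − 3 = 109, 168 − 3 = 165 and 392 − 7 = 385 days. These clear 105, 161 and 364 days, so every in-window completer in the arms concerned passes.
- Keep last active dose plus interval.
- In the discontinuer lines, restrict 10.1.1 to doses and stops in the Initial Treatment Period and 10.1.2 to those before Week 24, each with a cap at the end of the period.

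The cost is SAP wording and table programming, with no new data. The drawback is that the category labels no longer match the nominal period lengths. The change does not alter the mixing of subjects in the BKZ Q4W and Total columns.

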10.1.2 Exposure through Week 24 (not including Week 24 Visit) for SS

Definitions for study medication duration (days) and time at risk (days) through Week 24 are provided as follows:

Study medication duration (days)

- Date of last dose of active medication prior to Week 24 Visit – date of first dose in the Initial Treatment Period + 28 days for bimekizumab Q4W/ +56 days for bimekizumab Q8W/ +14 days for adalimumab.

Note: If date of last dose of active medication prior to Week 24 + 28 days/ 56 days/ 14 days extends to a date beyond the date of the first dose on or after Week 24, then this calculation reverts to:

- Date of first dose on or after Week 24 – date of first dose in the Initial Treatment Period + 1.

Note: For subjects who die during the first 24 weeks, if date of last dose of active medication prior to Week 24 + 28 days/ 56 days/ 14 days extends to a date beyond the date of death, then this calculation reverts to:

- Date of death – date of first dose in the Initial Treatment Period + 1.

For subjects who permanently discontinue study treatment:

- Date of last dose of active medication – date of first dose + 28 days/ 56 days/ 14 days
- Note: If date of last dose of active medication + 28 days/ 56 days/ 14 days extends to a date beyond the final visit date (including PEOT, but not including SFU), then this calculation reverts to:

Final visit date (including PEOT, but not including SFU) – date of first dose + 1.

Time at risk (days)

- For subjects who complete through Week 24 and continue beyond Week 24: Date of first dose on or after Week 24 – date of first dose in Initial Treatment Period + 1.
- For subjects who discontinue prior to Week 24 visit, use the minimum of the following:
 - Date of last dose prior to Week 24 – date of first dose in the Initial Treatment Period + 140 days.
 - The total number of days up to Week 24.
 - Date of last clinical contact – date of first dose in the Initial Treatment Period + 1.
- For subjects who die prior to Week 24 visit: Date of death – date of first dose in Initial Treatment Period +1.

10.1.3 Exposure during the initial and maintenance period for BKZ Set

Definitions for study medication duration (days) and time at risk (days) through initial and maintenance treatment period are provided as follows:

For subjects randomized to BKZ Q4W/Q4W:

Study medication duration (days)

- Date of last dose of bimekizumab – date of first dose + 28 days

Note: If date of last dose of bimekizumab+ 28 days extends to a date beyond the final visit date (including PEOT, but not including SFU), then this calculation reverts to:

- Final visit date (including PEOT, but not including SFU) – date of first dose + 1.

Note: For subjects who die, if date of last dose of bimekizumab+ 28 days extends to a date beyond the date of death, then this calculation reverts to:

- Date of death – date of first dose + 1.

Time at risk (days):

- For subjects who continue into an open-label study (and, therefore, do not have the SFU visit in the feeder study): Final visit date – date of first dose + 1.
- For subjects who die prior to the final visit: Date of death – date of first dose + 1.
- For all other subjects, use the minimum of the following:
 - Date of last dose – date of first dose + 140 days.
 - Date of last clinical contact – date of first dose + 1.

Note: This group could include subjects who discontinue early, subjects who complete the Maintenance Period as scheduled but choose not to continue into an open-label study, or subjects who are ongoing in the SFU period at the time of the data snapshot.

For subjects randomized to BKZ Q4W/Q8W:

Study medication duration (days)

- Initial Treatment Period (attributed to BKZ Q4W)
 - Date of last dose of bimekizumab in the Initial Treatment Period – date of first dose in the Initial Treatment Period + 28 days

Note: If date of last dose of bimekizumab in the Initial Treatment Period + 28 days extends to a date beyond the date of the first dose in the Maintenance Treatment Period, then this calculation reverts to:

- Date of first dose in the Maintenance Treatment Period – date of first dose in the Initial Treatment Period + 1.

Note: For subjects who die during the Initial Period, if date of last dose of bimekizumab in the Initial Treatment Period + 28 days extends to a date beyond the date of death, then this calculation reverts to:

- Date of death – date of first dose in the Initial Treatment Period + 1.

- Maintenance Treatment Period (attributed to BKZ Q8W)
 - Use the study medication duration algorithm described for Maintenance Treatment Period in 10.1.4.
- Initial and Maintenance Treatment Period combined (attributed to BKZ Total)
 - Date of last dose of bimekizumab – date of first dose + 28 days (if last dose was in Initial Period) or 56 days (if last dose was in Maintenance Period)

Note: If date of last dose of bimekizumab + 28 days (if last dose was in Initial Period) or 56 days (if last dose was in Maintenance Period) extends to a date beyond the final visit date (including PEOT, but not including SFU), then this calculation reverts to:

- Final visit date (including PEOT, but not including SFU) – date of first dose + 1.

Note: For subjects who die, if date of last dose of bimekizumab + 28 days (if last dose was in Initial Period) or 56 days (if last dose was in Maintenance Period) extends to a date beyond the date of death, then this calculation reverts to:

- Date of death – date of first dose + 1.

Time at risk (days):

- Initial Treatment Period (attributed to BKZ Q4W)
 - Date of first dose in Maintenance Treatment Period – Date of first dose in Initial Treatment Period + 1 (Note, this assumes that anyone in this category completes the Initial Treatment Period and doses in the Maintenance Treatment Period).
- Maintenance Treatment Period (attributed to BKZ Q8W)
 - Follow the time at risk algorithm described for the Maintenance Treatment Period in 10.1.4.
- Initial and Maintenance Treatment Period combined (attributed to BKZ Total)
 - For subjects who continue into an open-label study (and, therefore, do not have the SFU visit in the feeder study): Final visit date – date of first dose + 1.
 - For subjects who die prior to the final visit: Date of death – date of first dose + 1.
 - For all other subjects, use the minimum of the following:
 - Date of last dose – date of first dose + 140 days.
 - Date of last clinical contact – date of first dose + 1.

Note: This group could include subjects who discontinue early, subjects who complete the Maintenance Period as scheduled but choose not to continue into an open-label study, or subjects who are ongoing in the SFU period at the time of the data snapshot.

For subjects randomized to ADA/BKZ Q4W:

Only the duration of Bimekizumab treatment will be derived over this period as the summaries produced are for the BKZ Set (not including any adalimumab treatment).

- Follow the study medication duration and time at risk algorithms described for the Maintenance Treatment Period in 10.1.4.

